1.2 Introduction to investigational treatment

1.2.1 Overview of deferasirox film-coated tablet

The new deferasirox film-coated tablet (FCT) formulation for oral administration is being developed due to the chronic nature of chelation therapy and the importance of patient compliance. The FCT, which will be used in this study, contains the same active substance of the iron chelator deferasirox (Exjade® company research code ICL670) but has been strength-adjusted to achieve comparable exposure to the currently approved dispersible tablet (DT). The FCT is available in 3 dose strengths (90 mg, 180 mg and 360 mg) and is dosed based on body weight. The FCTs can be taken with or after a light meal.

1.2.1.1 Clinical experience with deferasirox

The efficacy and safety of deferasirox have been evaluated in a large prospective clinical trials program that has generated long-term data in patients with transfusional iron overload from a variety of transfusion-dependent anemias. Long-term studies (up to 5 years) in patients aged ≥ 2 have demonstrated that deferasirox, administered at doses of 10-40 mg/kg/day effectively reduce or maintain total body iron as assessed by serum ferritin or liver iron concentration (Cappellini et al 2011). Deferasirox was also shown to prevent or reduce cardiac iron overload in patients with thalassemia major as evidenced by changes in T2* cardiac MRI (Pennell et al 2010, Pennell et al 2011, Pennell et al 2012, Pennell et al 2014) and to be associated with improvement in liver pathology as evidenced by biopsy-assessed Ishak fibrosis staging and necro-inflammatory scores (Deugnier et al 2011), as well as improvement in hematopoietic parameters in myelodysplastic syndrome (MDS) patients using the International Working Group 2006 criteria (Gattermann et al 2012, List et al 2012). Improvements in hematopoietic parameters were also seen in patients with Aplastic Anemia (Lee et al 2013). Moreover, the data accumulated to date have well characterized the safety profile of deferasirox across all age groups and for a wide range of transfusion-dependent anemias including β-thalassemia, sickle cell disease, and MDS, indicating that the vast majority of adverse events are mild to moderate in severity and manageable with dose adjustments or interruptions. In patients with non-transfusion dependent thalassemia and iron overload, deferasirox at starting doses of 5 and 10 mg/kg/day with dose escalation up to 20 mg/kg/day was shown to reduce iron overload as evidenced by significant decreases in liver iron concentration and serum ferritin and with an overall safety profile comparable to placebo (Taher et al 2012). Continued treatment with up to 2 years resulted in continuous decrease in iron overload (Taher et al 2013). A new FCT formulation, containing the same deferasirox drug substance as the DT formulation has been developed. As of 31 May 2017, the FCT has been approved in several countries worldwide including the US, European Union, Canada and Switzerland under the name Jadenu or Exjade. The currently available limited

Protocol No. CICL670AIC04

clinical trial data with the new formulation, suggests a safety and efficacy profile that is consistent with the known profile of the DT deferasirox formulation. Hence, the continuously accumulating and available data to date confirm the favorable benefit-risk profile of deferasirox in patients with transfusional iron overload and those with non-transfusion dependent thalassemia.

2 Rationale

2.1 Study rationale and purpose

The availability of deferasirox DT (Exjade®) as a once-daily oral chelation treatment provided patients with a treatment that was a significant improvement over parenteral DFO therapy. This was confirmed in studies that measured satisfaction and QoL of oral vs. parenteral chelation (Cappellini et al 2007, Osborne et al 2007). Novartis is currently developing a deferasirox FCT with the same active substance as the deferasirox DT but with modified excipients.

After strength-adjustment, the new formulation was shown to achieve the same overall exposure (AUC_{last} and AUC_{inf}) as the currently approved DT formulation in a single-dose healthy volunteer study (ICL670F2102); the peak serum concentrations (C_{max}) were approximately 30% higher. In addition, a food effect study (ICL670F2103) indicated that the FCT can be taken with a light meal (the current deferasirox DT has to be taken on an empty stomach, at least 30 mins before a meal).

Thus, the FCT formulation has the advantage of more favorable pharmacokinetic properties (a reduced food effect and a more predictable dose-exposure relationship in clinical practice), better palatability, and a more convenient mode of administration compared to the currently available DT formulation. It is intended to be used for all currently approved deferasirox indications. Thus, the new FCT formulation could represent a significant improvement in patient care and support compliance with chelation therapy.

• Study CICL670F2201 was a randomized, open-label, multicenter, 2-arm, phase II study initiated to: Assess the safety of the DT and the FCT formulations in patients with transfusion-dependent thalassemia or MDS (very low, low or intermediate risk) treated over 24 weeks

The present protocol describes study CICL670AIC04 "Open-label, multicenter, single arm, 24-month, phase III study to collect additional safety and efficacy data with deferasirox film-coated tablets in patients completing study CICL670F2201", which aims to:

- Provide patients enrolled and completing 24 weeks of treatment in study CICL670F2201, the possibility to have additional treatment with the deferasirox FCT.
- Collect additional longer term data on the safety and the tolerability of the deferasirox FCT.
- Collect efficacy data on the deferasirox FCT in reduction or maintenance of iron burden as measured by serum ferritin level.

2.2 Rationale for the study design

This is an open-label, multicenter, single arm, phase III study that aims to provide additional drug exposure following study ICL670F2201, which is a randomized, open-label, multicenter, 2-arm, phase II study.

Two anemia types, transfusion-dependent thalassemia and MDS (very low, low or intermediate risk), were chosen for enrollment in study CICL670F2201. As transfusion-dependent thalassemia patients are more commonly children/adolescents while MDS patients are mostly adults and elderly, the population selected for CICL670F2201 allowed inclusion of patients from all deferasirox DT approved age groups. However, not more than 50% of MDS patients per arm were included in CICL670F2201. Patients assigned to either the deferasirox DT or deferasirox FCT arm and who completed the study period of 24 weeks are allowed to participate in this study. Patients who have withdrawn prematurely from CICL670F2201 will not be enrolled. Patients with a lag period between completion of CICL670F2201 and enrollment in this study can still be enrolled even if they had to switch to DT or other chelation therapy in this period.

The treatment duration of 24 weeks in CICL670F2201 is considered sufficient to assess the safety, pharmacokinetics (PK) and patient reported outcomes (PRO) of the 2 formulations. Previous studies of pediatric and adolescent patients have demonstrated differences in iron chelation medication compliance within this time period (Jordan et al 2012, Alvarez et al 2009). Long-term safety, tolerability, and efficacy will be assessed as objectives of this current study.

Overall safety is the primary objective of the current study and will be addressed by measuring the frequency and severity of adverse events (AEs) and changes in laboratory values. Time points for assessing laboratory values have been chosen based on the current labeling for deferasirox DT (Exjade[®]) in order to be as close as possible to the daily practice in administering the study treatment.

Recognizing that it is important to allow patients to continue their therapy under a controlled, even if less frequent monitoring plan, this multi-center, open-label study has been designed to provide additional supply of deferasirox FCT to patients recruited in Region Europe sites in study CICL670F2201 through a Novartis ORE-sponsored study, provided the patients have completed the CICL670F2201 study and are tolerating treatment.

2.3 Rationale for dose and regimen selection

Deferasirox FCT is available in 3 dose strengths (90, 180 and 360 mg). In CICL670F2201, all ICT naïve patients randomized to the study received a deferasirox DT starting dose of 20 mg/kg/day, or the equivalent FCT starting dose of 14 mg/kg/day. All iron chelation pre-treated patients received deferasirox DT or an equivalent FCT starting dose corresponding to their pre-washout dose. In CICL670F2201, patients on DT formulation were allowed dose adjustments with \pm 5 to 10 mg/kg/day, but no more than 40 mg/kg/day while patients on FCT formulation were allowed dose adjustments with \pm 3.5 to 7 mg/kg/day, but no more than 28 mg/kg/day.

At the start of this study, the following will occur:

- Patients continuing directly from the CICL670F2201 study who were originally randomized to the deferasirox FCT formulation will continue treatment at the same dose they were assigned at the end of the CICL670F2201 study.
- Patients continuing directly from the CICL670F2201 study who were originally assigned to the deferasirox DT formulation will be switched to the deferasirox FCT formulation and will be assigned a deferasirox FCT dose equivalent to the deferasirox DT dose they were assigned at the end of CICL670F2201 study (Appendix 14.2).
- Patients completing the CICL670F2201 study who had switched to commercially available DT or other ICT will have to undergo a 5-day washout period and then use an equivalent FCT starting dose corresponding to their pre washout iron chelator dose.

Dose adjustment for better treatment effects based on serum ferritin levels and investigator's judgment, will be allowed if necessary every 3 months, with \pm 3.5 to 7 mg/kg/day, but no more than 28 mg/kg/day.

2.4 Rationale for choice of combination drugs

Not applicable.

2.5 Rationale for choice of comparators drugs

Not applicable.

2.6 Risks and benefits

The first worldwide marketing authorization for deferasirox was received on 02-Nov-2005 (International Birth Date) in United States (US). Deferasirox is approved in over 100 countries worldwide for the treatment of transfusional hemosiderosis in patients 2 years of age and older.

Deferasirox is available as a DT containing 125, 250, or 500 mg of drug substance under Exjade[®] brand name. In certain countries, deferasirox is available as DT containing 100 or 400 mg and as FCT containing 90, 180 or 360 mg of drug substance. In addition, granules corresponding to an amount equivalent to 90, 180, 360 mg and 400 mg of drug substance have also been developed. As of 31-May-2017, the FCT has been approved in several countries worldwide including the US, European Union, Canada and Switzerland under the name Jadenu or Exjade. Granules have been approved in the US and Japan, and received CHMP Opinion in European Union.

Approximately, 8 121 subjects have received deferasirox in clinical trials as of 31-Oct-2016. The cumulative patient exposure since the International Birth Date of the product is estimated to be approximately 335 128 patient-treatment years. Although reports of hypersensitivity, pancreatitis, toxic epidermal necrolysis and rare fatal outcomes of renal events are currently being incorporated into the core data sheet and prescribing information. The benefit-risk profile for deferasirox remains positive for the treatment of iron overload and justifies unaltered continuation of the development program.

The risk to subjects in this trial may be minimized by compliance with the eligibility criteria and study procedures, close clinical monitoring, specific dose modification (for patients who

do not tolerate the protocol-specified dosing schedule) and stopping rules (refer Section 6 for details).

3 Objectives and endpoints

Objectives and related endpoints are described in Table 3-1 below.

Table 3-1 Objectives and related endpoints

Objective	Endpoint	Analysis
Primary		Refer to Section 10.4
To evaluate the overall safety of deferasirox FCT formulation in patients with transfusion-dependent thalassemia or MDS at very low, low or intermediate risk	Overall safety, as measured by frequency and severity of AEs and changes in laboratory values of interest i.e. serum creatinine and creatinine clearance	
Secondary		Refer to Section 10.5.1
To evaluate efficacy of deferasirox FCT on serum ferritin levels (decrease or maintenance, according to the individual therapeutic goal).	Absolute and relative change of serum ferritin level over time	

Abbreviations: FCT=film-coated tablet; MDS=myelodysplastic syndrome

4 Study design

4.1 Description of study design

This is an open-label, multicenter, single arm, 24-month, phase III study aimed at collecting additional data on safety and tolerability as well as data on efficacy of the FCT formulation in patients with transfusion-dependent thalassemia or MDS (very low, low or intermediate risk) when treated for more than 24 weeks in CICL670F2201. It is a pre-requisite for the patient to provide written consent for participation in this study. This must be in place prior to performing any study-related procedures or assessments, including those described at the Screening Visits (Table 7-1).

Patients from Region Europe participating sites in study CICL670F2201 who have completed the 24-week treatment period with ongoing tolerance to deferasirox (in the Investigator's opinion) and fulfilling all other eligibility criteria (Section 5) will be given the opportunity to continue study treatment and follow-up assessments in this study. This will include patients from Region Europe who completed 24-weeks of treatment with either deferasirox FCT or deferasirox DT in CICL670F2201; and patients with a lag period between completion of CICL670F2201 and start of this study i.e. those patients who completed CICL670F2201 and have already switched to commercially available deferasirox DT or another ICT.

In CICL670F2201, iron-chelation naïve patients were assigned either deferasirox DT 20 mg/kg once daily or deferasirox FCT 14 mg/kg once daily. All iron chelation pre-treated

patients were assigned a deferasirox DT or an equivalent FCT starting dose corresponding to their pre-washout dose. At the start of this study, the following will occur:

- Patients continuing directly from CICL670F2201 who were originally randomized to the deferasirox FCT formulation will continue treatment at the same dose they were assigned at the end of CICL670F2201.
- Patients continuing directly from CICL670F2201 who were originally assigned to the deferasirox DT formulation will be switched to the deferasirox FCT formulation and will be assigned a deferasirox FCT dose equivalent to the deferasirox DT dose they were assigned at the end of CICL670F2201 (Appendix 14.2).
- Patients completing CICL670F2201 who had switched to commercially available DT or other ICT will have to undergo a 5-day washout period and then use an equivalent FCT starting dose corresponding to their pre washout iron chelator dose.

Study treatment should be administered by the patient once per day. Following enrollment (Visit 3/Day 1) patients will return to the site at 2 week intervals until Visit 5 (Month 1). Thereafter, scheduled visits will be monthly (please refer Table 7-1 for study visit evaluation schedule). Patients may return to the study center more frequently at the physician's discretion as clinically indicated or as per standard of care. Serious adverse events (SAEs) will be reported to the Novartis safety database within 24 hours of investigator or treating physician's knowledge of the event from the time the patient has signed informed consent until at least 30 days after the patient stopped study treatment. All other assessments are performed as per standard of care at the site and will not be captured in the eCRF.

Patients who discontinue study treatment before completing the study should be scheduled for a visit within 7 days after the last dose, at which time all of the assessments listed for the end of treatment (EOT) visit (i.e. Month 24). The planned duration of treatment in this study is for a maximum of 24 months.

[figure not shown]

Figure 4-1 Study design

DT = Dispensible tablet FCT = Film-coated tablet EOT = End of treatment

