7.1 Study flow and visit schedule

Table 7-1 lists all of the assessments and indicates with an "X", the visits when they are performed.

Patients should be seen for all visits to perform the scheduled assessments on the designated day, or as close to is as possible, i.e., not exceeding \pm 7 days. In this clinical trial, a week is 7 calendar days. Visits should be planned respective to Visit 3, rather than in relation to the previous visits.

All data obtained from these assessments must be supported in each patient's source documentation. No eCRF will be used as a source document. The table indicates which data are entered into the database (D) or remain in source documents only (S) (column category).

Table 7-1 Visit evaluation schedule

	Category	Protocol section	Screening	(z visits > 1week apart)¹							Tr	eatme	ent Pe	riod						End of Treatment	Safety Follow- up
Visit no.			1	2	3	4	5	6	7	8	9	10	11	12	13	14	15	16	17 to 27	28²	
Study month			-2	2W	D1	W2	M1	M2	М3	M4	М5	М6	М7	M8	M9	M10	M11	M12	M13 to M23	M24 or Within 7 days of last dose	30 days after last dose
Informed consent	(D)	7.1.1	Х																		
Inclusion/ exclusion criteria	(D)	7.1.1.1	Χ	Х																	
History of disease	(D)	7.1.1.3	Χ																		
Demography	(D)	7.1.1.3	Χ																		
Relevant medical history/current medical conditions	(D)	7.1.1.3	X																		
Prior chelation therapy	(D)	7.1.1.3	Х																		
Transfusion/RBC History	(D)	7.1.1.3	Х																		
Transfusions received	(D)	7.1.3	Х		Х	Х	Х	Х	Х	Х	Х	Х	Х	Х	Х	Х	Χ	Χ	Х	Х	
Physical exam	(S)	7.2.2.1	Х		Х	Χ	Х	Х	Х	Х	Х	Х	Х	Х	Х	Χ	Χ	Χ		Х	
Weight ³	(D)	7.2.2.3	Х		Χ	Χ	Х	Χ	Χ	Х	Х	Х	Х	Χ	Χ	Χ	Χ	Χ	Χ	Х	
Height	(D)	7.2.2.3	Х																		
Vital signs	(D)	7.2.2.2	Х	Х	Χ	Х	Х	Х	Х	Х	Х	Х	Х	Χ	Χ	Χ	Χ	Χ	Χ	Х	
Ocular exam⁴	(D)	7.2.2.4	Х															Χ		Х	
Audiometry ⁴	(D)	7.2.2.4	Х															Χ		Х	
ECG	(D)	7.2.2.7.1	Х															Х		Х	
Chest X-ray (if clinically indicated) ⁵	(D)	7.2.2.6	Х																		

	Category	Protocol section	Screening	apart)¹							Tı	eatme	ent Pe	riod						End of Treatment	Safety Follow- up
Visit no.		_	1	2	3	4	5	6	7	8	9	10	11	12	13	14	15	16	17 to 27	28 ²	
Study month			-2	2W	D1	W2	M1	M2	М3	M4	M5	М6	М7	M8	М9	M10	M11	M12	M13 to M23	M24 or Within 7 days of last dose	30 days after last dose
Prior and Concomitant medications	(D)	6.4	Х	х	х	х	Х	Х	Х	Х	Х	Х	Х	Х	Х	Х	х	Х	Х	Х	
Adverse events	(D)	7.2.2	Х	Х	Х	Χ	Х	Х	Х	Х	Х	Х	Х	Х	X	Χ	Х	Х	Х	Х	Х
Laboratory assessments ⁶ -Blood																					

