8.1 Adverse events

8.1.1 Definitions and reporting

An AE is defined as the appearance of (or worsening of any pre-existing) undesirable sign(s), symptom(s), or medical condition(s) that occur after signed informed consent has been obtained from the patient/legal patient representative.

Abnormal laboratory values or test results occurring after informed consent constitute AEs only if they induce clinical signs or symptoms, are considered clinically significant, require therapy (e.g., hematologic abnormality that requires transfusion or hematological stem cell support), or require changes in study medication(s).

Except for screening failures, AEs that begin or worsen after informed consent should be recorded in the AE eCRF. Conditions that were already present at the time of informed consent should be recorded in the Relevant Medical History/Current Medical Conditions eCRF page. Adverse event monitoring should be continued for at least 30 days following the last dose of study treatment. Adverse events (including laboratory abnormalities that constitute AEs) should be described using a diagnosis whenever possible, rather than individual underlying signs and symptoms. When a clear diagnosis cannot be identified, each sign or symptom should be reported as a separate AE.

Severity of AEs will be assessed as mild, moderate, or severe. Information about any deaths (related to an AE or not) will also be collected using an EOT form.

The occurrence of AEs should be sought by non-directive questioning of the patient during the screening process after signing informed consent and at each visit during the current study. Adverse events also may be detected when they are volunteered by the patient during the screening process or between visits, or through physical examination, laboratory test, or other assessments. As far as possible, each AE should be evaluated to determine:

- 1. The severity grade (mild, moderate, or severe).
- 2. Its duration (Start and end dates or Ongoing at End of Study).
- 3. Its relationship to the study treatment (Reasonable possibility that AE is related: No, Yes).
- 4. Action taken with respect to study treatment (none, dose adjusted, temporarily interrupted, permanently discontinued, unknown, not applicable).
- 5. Whether medication or therapy was given (no concomitant medication/non-drug therapy, concomitant medication/non-drug therapy).
- 6. Whether it is serious, where a SAE is defined as in Section 8.2.1.

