9.3 Data collection

For studies using Electronic Data Capture (EDC), the designated investigator staff will enter the data required by the protocol into the eCRF. The eCRFs have been built using fully validated secure web-enabled software that conforms to 21 CFR Part 11 requirements, Investigator site staff will not be given access to the EDC system until they have been trained. Automatic validation programs check for data discrepancies in the eCRFs and, allow modification or verification of the entered data by the investigator staff.

The Principal Investigator is responsible for assuring that the data entered into eCRF is complete, accurate, and that entry and updates are performed in a timely manner.

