2.3.2 Baseline and post-baseline definitions

The baseline value for efficacy and safety variables is the last available, non-missing, (scheduled or unscheduled) value collected prior to first administration of study treatment on Day 1 of this study (or the first date when a non-zero actual dose of study drug was administered), unless otherwise stated.

Some baseline assessments may be recorded on the day of the baseline visit (Visit 3/Day 1). However the time of each of these assessments may not be recorded in the eCRF. In this case, only the assessments which, according to the protocol, should have been conducted pre-dose on Day 1 will be assumed to have been done prior to administration of study treatment on Day 1 when deriving baseline values recorded on the day of the baseline visit (Visit 3/Day 1).

All data collected after baseline (see Section 2.3.1 for definition of baseline date) are defined as post-baseline.

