2.9.3 Laboratory data

Hematology, serum chemistry, and urinalysis parameters will be presented using standard international (SI) units and the severity grade calculated using the low/normal/high classifications based on laboratory normal ranges, and for selected parameters by notable/extended ranges.

Raw values as well as absolute and relative change from baseline values for hematology, biochemistry, and urinalysis laboratory parameters will be summarized descriptively by visit (see Table 2-2 for time windows definition).

The following summaries will be generated separately for hematology, biochemistry, and urinary laboratory tests:

- shift tables using normal/notable/extended ranges to compare baseline to the worst ontreatment value
- listing of all laboratory data with values flagged to show the corresponding normal/notable/extended ranges

All data, including data from unscheduled visits, will be considered when identifying abnormal values.

Shift tables based on normal ranges to compare baseline to the worst post-baseline value will be provided by parameter for hematology, biochemistry, and urinary laboratory data.

A similar shift table will be provided based on notable/extended ranges for key safety laboratory parameters defined in Section 10.5.2.2 (Clinical Trial Protocol CICL670AIC04 Amended Protocol Version 1, 25 October 2017).

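### Protocol 4.1 bars all assessments other than SAE reports from the eCRF, contradicting Table 7-1, 8.1.1 and 9.3; applied only to extra visits, it still withholds unscheduled laboratory values that the SAP uses

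*Protocol*

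**What the plan says.** Protocol 4.1 sets out the visit schedule, refers to Table 7-1, and then adds: "Patients may return to the study center more frequently at the physician's discretion as clinically indicated or as per standard of care". The next sentence covers SAE reporting within 24 hours. The one after that reads: "All other assessments are performed as per standard of care at the site and will not be captured in the eCRF". Nothing in it says which assessments the others are being distinguished from.

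Other sections state the opposite rule:

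- Protocol 7.1, introducing Table 7-1: "The table indicates which data are entered into the database (D) or remain in source documents only (S) (column category".
- Protocol 8.1.1: "Except for screening failures, AEs that begin or worsen after informed consent should be recorded in the AE eCRF".
- Protocol 9.3: "the designated investigator staff will enter the data required by the protocol into the eCRF".

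The SAP expects off-schedule results to be in the database. Section 2.9.3 says of the laboratory tables: "All data, including data from unscheduled visits, will be considered when identifying abnormal values". Section 2.3.3.2 takes the worst post-baseline value from all on-treatment values whatever their window. For by-visit summaries it picks the result nearest the planned day.

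**The concern.** Safety is the primary objective, and there is no comparator and no hypothesis test. The descriptive tables are therefore the whole result, and they are only as good as the capture rule behind them. A site that followed the sentence as worded would enter SAE reports and nothing else. A site that tied it to the extra visits would enter scheduled results and leave out the others. Two sites could both believe they were compliant and hand over different data.

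The second behaviour is the more plausible, and its effect is selective. Off-schedule samples are mostly taken because something looked abnormal, so leaving them out tends to make the laboratory safety picture look milder.

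**Working it through.** There is no sample size, power or error rate to reproduce. The check compares the passages and adds some visit-day arithmetic.

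**1. Capture column.** By hand count, Table 7-1 has 31 assessment rows. Thirty are marked (D); one, physical examination, is marked (S). AEs, hematology, biochemistry, ferritin, creatinine, creatinine clearance and urine protein/creatinine ratio are all (D).

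**2. Three readings of the sentence.**

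| Source | Everything except SAE reports | Extra visits only | Only what the protocol does not require |
|---|---|---|---|
| Table 7-1 | Contradiction | None; the table has no unscheduled-visit column | None |
| Protocol 8.1.1 | Contradiction | Only if taken to cover AEs found at those visits | None |
| Protocol 9.3 | Contradiction | Only for repeats the protocol calls for | None |
| SAP 2.3.3.2 and 2.9.3 | Contradiction | Contradiction | Discretionary tests only |

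The text does not say which reading is meant.

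**3. Does the protocol generate off-schedule results?** Yes.

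- 6.3.1.2: a raised creatinine is repeated at the next visit or when clinically indicated.
- 6.3.1.4: dose rules use two urine samples at least 48 hours apart.
- 6.3.2: follow-up is at least weekly for 4 weeks after an interruption or discontinuation for an AE or abnormal laboratory value. Four weeks give at least 4 contacts. Once visits are monthly, that span contains about one scheduled visit, so about 4 − 1 = 3 contacts fall off schedule. Section 6.3.2 does not say that each contact includes a blood or urine sample.

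**4. Which analyses are exposed?**

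- Worst on-treatment value: dropping results can only leave the recorded worst value the same or milder.
- Notable and extended ranges (Protocol Table 10-1): platelets, neutrophils, ALT and AST are classified without a repeat, so a short-lived peak seen only at an extra visit is lost.
- Creatinine, clearance and urine protein/creatinine ratio need two consecutive values at least 7 days apart. A missing high repeat can remove a classification. Less often, a missing normal value between two high ones can create one.

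**5. Can scheduled visits confirm on their own?** In the SAP's 28-day months, Month 1 is Day 29 and Month 2 is Day 57: 57 − 29 = 28 days. Protocol 7.1 allows 7 days either side of each visit, so the shortest monthly gap is 28 − 7 − 7 = 14 days, which exceeds 7. The early visits (Days 1, 15 and 29) are nominally 14 days apart. Two consecutive scheduled values can therefore satisfy the rule, unless the value has recovered by the second.

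**6. Reach into the primary laboratory variables.** SAP 2.6.1 names changes at Month 6 (Days 156–183, target 169) and Month 12 (Days 324–351, target 337). An unscheduled value enters only if it is nearer the target, is equally near and later, or the scheduled value is missing.

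**7. Scale.** SAP Section 3 plans at most 58 patients: 1/58 = 1.7%. A smaller Safety Set makes each patient count for more.

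**The case against.** The strongest reply is that no site would take the sentence literally. The same paragraph points to Table 7-1, and Sections 8.1.1, 6.6.3.2 and 9.3 are more specific and require entry of AEs, dosing and protocol data. SAP 2.8.1 also describes ferritin being recorded in EDC. A sensible reader may take the sentence to mean assessments outside the protocol. This stands to a large extent. A reader might infer that non-serious AE, laboratory and ferritin data would be lost; the documents do not support that, because sites would have to ignore all of these sections.

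A reader might also infer that a confirmed renal event would vanish once the dose was changed and the value recovered. Protocol 8.1.1 and 8.1.2.1 make a laboratory abnormality that requires a change in study medication an AE, and the reason for a dose change is recorded (6.1.1, 6.6.3.2). The event stays in the AE analysis; only its place in the notable-range table is at risk.

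Nor do unscheduled confirmatory values form a minimum loss to the primary endpoint. Table 10-1 sits under other safety objectives (Protocol 10.5.2), and step 6 shows how narrow the route into the Month 6 and 12 summaries is.

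Finally, SAP 2.3.2 takes as baseline the "last available, non-missing, (scheduled or unscheduled) value collected prior to first administration" of study treatment, which might suggest that baseline is affected too. The extra visits in 4.1 are described as following enrollment at Visit 3/Day 1, so on that reading the pre-dose value is untouched.

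None of this reconciles the extra-visit reading with SAP 2.3.3.2 and 2.9.3. Abnormalities that trigger no dose change, treatment or symptom, and are not judged clinically significant, are not AEs and have no second route into the data.

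**Conclusion.** The sentence is wrong as written. It contradicts the (D) column of Table 7-1, Section 8.1.1 and Section 9.3. Confined to the extra visits, it conflicts with the SAP's worst-value, windowed, abnormal-flag and notable/extended-range analyses.

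The likely consequence is inconsistent entry of post-baseline unscheduled results between sites, with transient laboratory abnormalities under-counted in the shift tables. The size cannot be estimated: the documents do not say how often extra tests are done or how quickly values recover. It depends on how sites read the sentence and on how the eCRF and its completion instructions handle unscheduled results, which the documents do not show. In a trial of at most 58 patients, a few missed cases would visibly change a percentage. A reader should not go further and conclude that the primary endpoint is compromised.

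**What to change.** Replace the sentence in Protocol 4.1 with:

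> All assessments marked (D) in Table 7-1, all AEs, and repeat or unscheduled results for the safety laboratory parameters analysed in the SAP (at least those in Section 10.4.1 and Table 10-1) are entered in the eCRF; other assessments, not required by this protocol, are not.

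Carry the same rule into the eCRF completion instructions. Before database lock, wherever a parameter has a value beyond a Table 10-1 limit, have data management ask the site whether later unscheduled results for it remain un-entered. Do not query for absent ALT or AST repeats, because Table 10-1 does not require a second value for them.

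The cost is one sentence, some extra data entry and a limited set of queries. Restricting the rule to the analysed safety parameters keeps other routine standard-of-care tests out of the database. No assessment, visit or treatment rule changes.
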